#### 7.6.5 BIOMARKERS

The biomarker α-fetoprotein (AFP) will be assessed at Baseline, at Day 1 of each cycle, and at the follow-up visit. Summary statistics for AFP levels and CFB in AFP levels will be provided for the ITT Population by treatment and visit. Between-treatment comparisons will be performed by visit using Analysis of Covariance (ANCOVA) with CFB as the dependent variable and Baseline as the covariate. Summary statistics for AFP and CFB in AFP will be provided for each level of Overall Response for the ITT Population by treatment. Distribution of Overall Response will be presented for subjects with AFP levels <20, 20-200, or >200 ng/mL and for subjects with AFP levels above or at most the pooled median by treatment and cycle; the percentages will be calculated using number of subjects within each category defined by AFP levels as the denominator for each treatment.

WBC A3AR expression will be assessed at Baseline and at Day 1 of each odd-numbered cycle. Summary statistics for WBC A3AR expression and CFB in WBC A3AR expression will be provided for the ITT Population by treatment and visit. Summary statistics for CFB in WBC A3AR expression will be provided for each level of Overall Response for the ITT Population by treatment. To assess the relationship between Overall Response and changes in WBC A3AR at each visit, the distribution of Overall Response will be presented for subjects with WBC A3AR less than the pooled median and for subjects with WBC A3AR at least the pooled median at each post-baseline visit.

#### 7.6.6 CHEMISTRY AND COAGULATION PARAMETERS

The following laboratory parameters will be examined as exploratory efficacy variables:

- alanine aminotransferase (ALT)
- albumin
- aspartate aminotransferase (AST)
- bilirubin (direct and total)
- International Normalized Ratio (INR)
- prothrombin time (PT).

The above variables and CFB for each variable will be summarized by treatment and visit for the ITT Population. Between-treatment comparisons will be performed by visit using ANCOVA with CFB as the dependent variable and the Baseline value of the variable as the covariate. These variables will be listed for the Safety Population with the other laboratory parameters.

#### 7.6.7 HEPATITIS VIRAL LOAD

Viral load for Hepatitis B Virus (HBV) and Hepatitis C Virus (HCV) for subjects with positive serology at Screening will be summarized using summary statistics for log-transformed values using the base 10 logarithm, which will be presented by treatment and visit for the ITT Population. Between-treatment comparisons will be performed by visit using ANCOVA with CFB for log-transformed values as the dependent variable and Baseline as the covariate. These variables (viral load (IU/mL) and log-transformed viral load) will be listed for the Safety Population. Any viral load recorded for subjects who do not have positive serology at Screening will not be included in tables but will be included in listings only.

#### 7.6.8 SUBGROUP ANALYSES

After unblinding, it was decided to perform various subgroup analyses of OS. The subgroup analyses will be performed by the following assessments at Screening or Baseline:

CP Score at Screening (7, 8, 7+8, or 9), Sex, ECOG PS at Screening (0 or 1+2).

AFP (≤400 ng/mL or >400 ng/mL) at Baseline,

Prior Locoregional therapy (HCC Prior Therapies of Radiation or

Chemoembolization =Yes, Otherwise =No),

EHS (Yes or No), PVT (Yes or No), and Either EHS or PVT (Yes or No),

History of HBV (Known history of HBV=Yes or No),

History of HCV (Known history of HCV=Yes or No),

Diagnostic Procedure (Cytology/histology or AASLD), and

Country (based on the first digit of the site number, given as Bulgaria=1, Serbia=2, Israel=3, Romania=5, or United States=7).

The subgroup analyses will be performed as univariate analyses within each level of the corresponding subgrouping variable. For each subgrouping variable, the between-treatment comparisons will be performed using the logrank test (Section 7.6.1). Each analysis will include the hazard ratio with the corresponding 95% confidence interval from proportional hazards model with no additional covariates and the p-value (Chi-Square), as described in Section 9. The subgroup analyses do not include a plot of each KM curve, except for the analyses by CP Score at Screening (CP=7, CP=8, or CP=7 or 8), and do not include the value of the KM curve at the median duration of therapy, provided in the analyses for the ITT Population.

History of viral hepatitis is recorded as "Yes, Hepatitis B"; "Yes, Hepatitis C"; "No"; or "Not known", with the date of diagnosis recorded for the first two responses, both of which are possible. If both of these responses are recorded, then the response for both History of HBV and History of HCV will be considered "Yes". Subjects with responses of "Not known" will be excluded from the subgroup analyses using history of viral hepatitis.

Subgroup analyses for other time-to-event variables or tumor response variables may be presented as further exploratory analyses after review.

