## 7.6.1 OVERALL SURVIVAL (OS)

Overall survival (OS) is the time from Baseline to death due to any cause. OS will be summarized in months, which will be obtained by dividing OS in days by 30 days/month. Subjects who are alive at last contact will be considered censored at the date of last contact. Summary statistics (25th percentile, median, and 75th percentile) will be determined using the Kaplan-Meier (KM) estimate of the survival function. These summary statistics will be listed to one decimal place, rounded down such as the SAS FLOOR function. The KM curve for OS will be presented. The value of the KM curve for OS at the median duration of therapy (Section 7.5.1) will be presented. The between-treatment comparison will be performed using the logrank test as the primary analysis. Between-treatment comparisons with respect to OS will be also performed using the proportional hazards model with AFP at Baseline and A3AR level at Baseline as covariates individually as secondary analyses, including the hazard ratio and the 95% confidence interval for the hazard ratios for both treatment and the covariate. Additional details are given in Section 9.

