#### 9. DIFFERENCES AND CHANGES FROM THE PROTOCOL

The protocol states that disease history includes duration of prior sorafenib therapy, reason(s) for discontinuation of sorafenib, and if applicable, nature of intolerability to sorafenib. The duration is not directly collected, but can be computed from the start and stop dates, as provided for all prior HCC therapies. The reasons(s) for discontinuation, including nature of intolerability, were not collected for prior HCC therapies, including sorafenib.

The protocol states that the listing of "dosing interruptions and dose reductions" will be provided. This listing is not provided, as these data were not specifically recorded, but are available as the "Action Taken" for AEs.

In the protocol, ITT Population is defined as "all subjects in the Safety Population who have any post-Baseline efficacy data, including Liver Chemistry Tests and/or INR on Day 8 of Cycle 1, or death or discontinuation due to disease progression at any time." According to SAP, ITT Population "is defined as all subjects in the Safety Population with any post-Baseline assessment recorded". The difference has no impact, especially since no subjects were excluded from the ITT Population.

Summaries of all safety variables by visit will be presented for visits at which there are at least 4 subjects in either treatment group. AEs, deaths, SAEs, and Discontinuation due to AE are not subject to this constraint. This restriction was not given in the protocol.

Summaries and analyses of efficacy variables by visit will be presented using visits through end of Cycle 11. Analyses of time to event (OS, TTP, and PFS) and Best Overall Response will not be restricted to visits through Cycle 11. This restriction was not given in the protocol.

Analyses of time to event (OS, TTP, and PFS) originally included summary statistics (25th percentile, median, and 75th percentile) from the KM estimate of the survival function and the value of the KM curve at the median duration of therapy. The between-treatment comparisons were performed using the logrank test. After unblinding, it was decided to include the hazard ratio with the corresponding 95% confidence interval from proportional hazards model with no additional covariates and the p-value (Chi-Square). The subgroup analyses of OS (Section 7.6.8) were not presented in the protocol.

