Time To Progression (TTP)	n	XX	XX
······o ··o · ··og··oocio··· (· · · · )	25th Percentile	XX.X	XX.X
	Median	XX.X	XX.X
	75th Percentile	XX.X	XX.X
	Value of KM at Median Duration (%)	XX.X	XX.X
	Number (%) observed events	xx (xx.x)	XX (XX.X)
	Number (%) censored	XX (XX.X)	XX (XX.X)
	P-value (LR)	0.xxx	λλ (λλ.λ)
Progression-free Survival (PFS)	n	XX	xx
1 Togression-nee ourvival (1 1 0)	25th Percentile	XX.X	XX.X
	Median	XX.X XX.X	XX.X XX.X
	75th Percentile	XX.X XX.X	XX.X XX.X
	Value of KM at Median Duration (%)	XX.X	XX.X
	Number (%) observed events	xx (xx.x)	xx (xx.x)
	Number (%) censored	xx (xx.x)	xx (xx.x)
D value (LD) -D value using the log	P-value (LR)	0.xxx	

P-value (LR) =P-value using the logrank test. KM=Kaplan-Meier

Baseline=Cýcle 1 Day 1

Percentages are calculated using the number of subjects in the ITT Population for each treatment as the denominator. For Median Duration, see Table 14.1.7.

HR=Hazard Ratio for Treatment from Proportional Hazards Model with Treatment and the specified covariate in the model

[figure not shown]
and P-value (PH) is the corresponding p-value (Chi-Square).

Source: Listing 16.2.5.1

Figure 14.2.1

Kaplan-Meier curve for OS

[figure not shown]
ITT Population

Source: Listing 16.2.5.1

Figure 14.2.2

Kaplan-Meier curve for TTP ITT Population

[figure not shown]

Source: Listing 16.2.5.1

Programming Note: Include number of patients at any month in the figure.

Figure 14.2.3

Kaplan-Meier curve for PFS
ITT Population

Source: Listing 16.2.5.1

Programming Note: Include number of patients at any month in the figure.

Table 14.2.2.1.1

Overall Response Using RECIST Criteria
ITT Population

		CF102	Placebo
Visit	Response, n (%)	(N=xx)	(N=xx)
Cycle 3 Day 1	CR	xx (xx.x)	xx (xx.x)
	PR	xx (xx.x)	xx (xx.x)
	SD	xx (xx.x)	xx (xx.x)
	PD	xx (xx.x)	xx (xx.x)
	Total	XX	xx
	ORR	xx (xx.x)	xx (xx.x)
	P-value	0.xxxx	` ,
	DCR	xx (xx.x)	xx (xx.x)
	P-value	0.xxxx	, ,
Cycle 5 Day 1	CR	xx (xx.x)	xx (xx.x)
	PR	xx (xx.x)	xx (xx.x)
	SD	xx (xx.x)	xx (xx.x)
	PD	xx (xx.x)	xx (xx.x)
	Total	XX	XX
	ORR	xx (xx.x)	xx (xx.x)
	P-value	0.xxxx	
	DCR	xx (xx.x)	xx (xx.x)
	P-value	0.xxxx	

Includes only assessments through Cycle 11.

CR=Complete Response, PR =Partial Response, SD =Stable Disease, PD=Progressive Disease

ORR=Objective Response Rate= proportion of subjects who have response of CR or PR

DCR=Disease Control Rate= proportion of subjects who have response of CR, PR, or SD

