Programming Notes: Continue for CP=8.

For CP=9, do not include P-value (LR), HR, 95% CI for HR, and P-value (PH) and only enter 0 for 'n' for Placebo.

Figure 14.2.7.1

Kaplan-Meier curve for OS
CP Score at Screening = 7
ITT Population

Source: Listings 16.2.3.1, 16.2.5.1

Programming Note: Use same structure for Figures 14.2.7.2 (OS, CP=8) and 14.2.7.3 (OS, CP= 7 or 8).

Table 14.2.7.2 Overall Survival (OS; months) by Sex ITT Population

		CF102	Placebo
Sex	Statistic	(N=xx)	(N=xx)
Male	n	XX	XX
	25th Percentile	XX.X	XX.X
	Median	XX.X	XX.X
	75th Percentile	XX.X	XX.X
	Number (%) observed events	xx (xx.x)	xx (xx.x)
	Number (%) censored	xx (xx.x)	xx (xx.x)
	P-value (LR)	0.xxx	
	HR	X.XX	
	95% CI for HR	(x.xx, x.xx)	
	P-value (PH)	0.xxx	
Female	n ` '	XX	XX
	25th Percentile	XX.X	XX.X
	Median	XX.X	XX.X
	75th Percentile	XX.X	XX.X
	Number (%) observed events	xx (xx.x)	xx (xx.x)
	Number (%) censored	xx (xx.x)	xx (xx.x)
	P-value (LR)	0.xxx	, ,
	HR `´	X.XX	
	95% CI for HR	(x.xx, x.xx)	
	P-value (PH)	0.xxx	

P-value (LR) =P-value using the logrank test.

Percentages are calculated using the number of subjects in the ITT Population in the specified subgroup category

for each treatment as the denominator.

HR=Hazard Ratio for Treatment from Proportional Hazards Model with Treatment as the only factor in the model and P-value (PH) is the corresponding p-value (Chi-Square). Source: Listings 16.2.3.1, 16.2.5.1

Table 14.2.7.3 Overall Survival (OS; months) by ECOG PS at Baseline ITT Population

		CF102	Placebo
ECOG PS	Statistic	(N=xx)	(N=xx)
0	n	xx	XX
	25th Percentile	XX.X	XX.X
	Median	XX.X	XX.X
	75th Percentile	XX.X	XX.X
	Number (%) observed events	xx (xx.x)	xx (xx.x)
	Number (%) censored	xx (xx.x)	xx (xx.x)
	P-value (LR)	0.xxx	
	HR	X.XX	
	95% CI for HR	(x.xx, x.xx)	
	P-value (PH)	0.xxx	
1 or 2	n	XX	XX
	25th Percentile	XX.X	XX.X
	Median	XX.X	XX.X
	75th Percentile	XX.X	XX.X
	Number (%) observed events	xx (xx.x)	xx (xx.x)
	Number (%) censored	xx (xx.x)	xx (xx.x)
	P-value (LR)	0.xxx	
	HR	X.XX	
	95% CI for HR	(x.xx, x.xx)	
	P-value (PH)	0.xxx	

P-value (LR) =P-value using the logrank test.
Percentages are calculated using the number of subjects in the ITT Population in the specified subgroup category for each treatment as the denominator.

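### No pooled overall-survival estimate accounts for Child-Pugh score, the unadjusted hazard ratio promised in SAP Section 9 has no table row, and the 28 post-unblinding subgroup tests carry no interaction test

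*SAP*

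**What the plan says.** **Pooled OS analyses.** SAP 7.6.1 states: "The between-treatment comparison will be performed using the logrank test as the primary analysis". It names no strata. The Cox models for OS use baseline AFP and baseline A3AR "as covariates individually as secondary analyses, including the hazard ratio". SAP Section 9 adds, for OS, TTP and PFS: "After unblinding, it was decided to include the hazard ratio with the corresponding 95% confidence interval from proportional hazards model with no additional covariates". Protocol 12.4.2 foresees Cox models to examine covariates but does not name Child-Pugh score.

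**Subgroup analyses.** SAP 7.6.8 opens: "After unblinding, it was decided to perform various subgroup analyses of OS". Section 9 confirms: "The subgroup analyses of OS (Section 7.6.8) were not presented in the protocol". The form is set out in 7.6.8: "The subgroup analyses will be performed as univariate analyses within each level of the corresponding subgrouping variable". Each level gets a logrank test and an unadjusted HR with 95% CI. Neither document plans a treatment-by-subgroup interaction test.

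**Shells.** The programming note to Table 14.2.7.1 reads: "For CP=9, do not include P-value (LR), HR, 95% CI for HR, and P-value (PH) and only enter 0 for 'n' for Placebo". In Table 14.2.1 the footnote defines: "HR=Hazard Ratio for Treatment from Proportional Hazards Model with Treatment and the specified covariate in the model". The OS block there prints one HR from the AFP model and one from the A3AR model. The TTP and PFS blocks end at the logrank p-value. Table 14.1.3 tabulates CP 7, 8 and 9 by arm at baseline.

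**Prognosis and randomization.** Protocol 4.3 and Appendix C link Child-Pugh to prognosis by class (A, B, C). Protocol 7.3 gives the 2:1 ratio and leaves further randomization detail to separate documents.

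**The concern.** Cirrhosis of Child-Pugh Class B is the eligibility-defining feature of the trial, and the shell indicates that one of the three scores within that class occurs in one arm only. CP=9 subjects on CF102 then enter the ITT HR without a same-score comparator. If score within Class B predicts survival, the unadjusted HR mixes the treatment effect with that imbalance and with any chance difference between arms in CP 7 versus 8. If CP=9 carries the worse prognosis, its contribution works against CF102. The pre-planned covariates do not address this, and A3AR is sampled at selected sites only (Protocol 9.2.9), so that model may not cover the whole ITT population.

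Two further gaps sit beside it. An estimate that Section 9 commits to has nowhere to be printed. And the subgroup tables offer many within-level p-values, which do not answer whether the effect differs between levels.

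**Working it through.** **1. The plan's own figure.** Inputs from Protocol 12.2: HR 0.5, two-sided 0.05, 80% power, 2:1 allocation, 75 deaths. Schoenfeld: d = (1.960 + 0.842)² / [(2/3)(1/3)(ln 0.5)²] = 7.85 / 0.1068 = 73.5, so 74. Power at 75 deaths: Φ(√(75 × 0.2222) × 0.693 − 1.960) = Φ(0.870) = 0.808. The stated 75 deaths and 80% reproduce.

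**2. Does any pooled OS estimate control for score?**
- Logrank: no stated strata.
- Cox with AFP, Cox with A3AR: score absent.
- HR added in Section 9: no covariates.
- CP=7+8 subset: removes CP=9 by restriction, but does not adjust for 7 versus 8.
- CP=7 and CP=8 separately: free of score imbalance, but not pooled.

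**3. Could zero CP=9 on placebo be chance?** Assuming 52:26 with no stratification, P = C(52,m)/C(78,m). For m = 3: (52·51·50)/(78·77·76) = 0.29. For m = 5: 0.12; m = 10: 0.013; m = 15: 0.001. Chance is plausible only if CP=9 subjects are few.

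**4. Size.** CP counts and hazards are not in the documents, so these are assumptions: 52/26 subjects, 75 deaths, true HR 0.5, exponential survival, placebo CP=7 median 3 months, uniform accrual over 18 months, CP=8 hazard equal to the square root of the CP=9 hazard (both relative to CP=7), CP 7 and 8 equally common in each arm, 8,000 runs per case. Entries are geometric-mean HR / power.

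| CP=9 on CF102 | CP=9 hazard | Unadjusted | CP-stratified | CP=7+8 subset |
|---|---|---|---|---|
| 3 | 1.5 | 0.503 / 77.6% | 0.493 / 77.4% | 0.494 / 78.4% |
| 3 | 2 | 0.512 / 76.1% | 0.491 / 78.2% | 0.497 / 78.5% |
| 5 | 1.5 | 0.508 / 76.4% | 0.491 / 77.3% | 0.494 / 78.2% |
| 5 | 2 | 0.523 / 73.7% | 0.488 / 78.5% | 0.498 / 77.7% |

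The reference with no CP effect and no CP=9 is 0.489 / 80.9%, so 0.49 is the small-sample baseline. The unadjusted shift is 0.014 to 0.034. Under no treatment effect the unadjusted HR is 1.00–1.04 and the stratified HR 0.99–1.00.

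**5. If CP=8 is also unbalanced** (5 CP=9 subjects, hazard 2). With CP=8 in 28/47 versus 10/26 (60% v 38%): unadjusted 0.559, stratified 0.489, CP=7+8 subset 0.535. With 19/47 versus 16/26 (40% v 62%): 0.488, 0.490, 0.463. A gap of 20 points or more in either direction has probability 0.087 under randomization.

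**6. What stratification uses.** Stratifying by 7/8/9 and fitting CP=7+8 stratified by 7/8 gave identical estimates, because a stratum without placebo subjects carries no treatment information.

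**7. Subgroup tests.** Count from 7.6.8: CP 7, 8, 7+8 (3); ten two-level factors (20); five countries (5); total 28. With no true effect, the chance of at least one p<0.05 is 1 − 0.95²⁸ = 0.76 if independent, and 0.64–0.66 in simulation with assumed prevalences. For a CP 7 versus 8 interaction with 75 deaths split equally: SE = √(4.5/37.5 + 4.5/37.5) = 0.490, where 4.5 = 1/[(2/3)(1/3)]. Power for a twofold ratio of HRs is Φ(0.693/0.490 − 1.96) = 0.29; simulation gave 0.28.

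**The case against.** The strongest reply is that the planned output already carries the information. Tables 14.1.3 and 14.2.7.1 give CP by arm, HRs with CIs for CP=7, CP=8 and CP=7+8, and a descriptive summary for CP=9. Comparing ITT with CP=7+8 shows much of the CP=9 influence. Inverse-variance pooling of the CP=7 and CP=8 HRs comes close to the stratified model: in a check of 1,000 runs the log HRs differed by a median of 0.002 and a 95th percentile of about 0.02. This stands. The added model gives a direct figure rather than otherwise unobtainable information.

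It also stands that prognosis is documented for classes only, and every subject is Class B. The only CP survival figures from the drug's earlier HCC trial run the other way (median OS 9.5 months in Class B, 7.2 in Class A; 19 subjects in all, so weak; Protocol 4.2.2). The subgroup analyses are openly disclosed as post-unblinding, and the proposed model is post hoc too.

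What does not fall away is the mismatch between Section 9 and Table 14.2.1, the absence of any directly reported score-controlled estimate, and the absence of interaction tests.

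A reader might infer that the ITT result is seriously distorted. A separate simulation with 5 to 15 CP=9 subjects at hazard 1.5 to 3 gives unadjusted HRs of 0.51 to 0.67. But the upper end needs numbers for which zero on placebo is very unlikely (0.013 for 10, 0.001 for 15), and the documents support neither those counts nor those hazards.

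**Conclusion.** The point holds as a gap in supportive analysis and reporting, of minor to moderate priority. No pooled OS estimate controls for CP score while the shell fixes CP=9 on placebo at zero. The effect is small under the assumed 3–5 CP=9 subjects with CP=8 balanced (HR 0.50–0.52 against 0.49). It could reach about 0.56 with a CP=8 gap of about 20 points, and its true size cannot be known from the documents.

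The missing rows for the unadjusted HR are a plain SAP-to-shell inconsistency that needs no assumption, and they affect OS, TTP and PFS alike. The 28 within-level tests are likely to include a chance finding and do not show whether the effect differs by subgroup.

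A reader might also infer that the primary test is invalid, that randomization failed or was unstratified, or that the subgroup work was concealed. None of these is supported. The pre-specified logrank test remains valid, randomization details lie in documents not available here, and the SAP states when the subgroup analyses were decided.

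**What to change.** 1. **SAP 7.6.1 and Table 14.2.1:** add one supportive ITT Cox model for OS, stratified by CP score at Screening (7, 8, 9) and labelled post hoc. State that CP=9 contributes no treatment information, so the estimate equals a CP=7+8 model stratified by 7 versus 8.
2. **Table 14.2.1:** add the unadjusted HR, 95% CI and p-value rows for OS, TTP and PFS that Section 9 calls for.
3. **SAP 7.6.8 and Tables 14.2.7.x:** head the tables post hoc and exploratory. Add a treatment-by-subgroup interaction p-value for CP (7 versus 8) and for each of the ten two-level factors, with a note on low power.
4. **SAP Section 9:** record these changes. The logrank test stays primary.

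**Cost.** Programming only, on data already collected. If CP score is not prognostic, stratifying costs about 2–4 points of power (81% to 77–79%); simulated two-sided type I error is 0.049–0.058. The CP interaction test has about 28% power for a twofold ratio of HRs. Eleven interaction tests still give a 46–47% simulated chance of at least one p<0.05 with no effect (1 − 0.95¹¹ = 43% if independent), so they too remain exploratory.

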#### 7.7 SAFETY ANALYSES

Safety data consist of adverse events (AEs), laboratory tests including thyroid functions, vital signs and weight, and physical examinations. Summaries of safety data will be conducted on all subjects in the Safety Population. Missing safety data will not be imputed. Summaries of all safety variables by visit will be presented for visits at which there are at least 4 subjects in either treatment group. Summaries of AEs, deaths, SAEs, and Discontinuation due to AE will not be restricted to visits with at least 4 subjects in either treatment group. All safety data will be listed.

#### 7.7.1 ADVERSE EVENTS

The original reported (verbatim) terms used by the Investigator to identify adverse events in the CRFs will be entered into the database and coded by Preferred Term using the Medical Dictionary for Regulatory Activities (MedDRA) coding dictionary (MedDRA MSSO, Reston, Virginia USA). Adverse events will then be grouped by MedDRA Preferred Term (PT) into frequency tables according to System Organ Classification (SOC).

An adverse event that started during the treatment period (on or after the day of the baseline visit) or that was present at Baseline and increased in severity during the treatment period will be considered a treatment-emergent adverse event (TEAE). Events ending prior to the day of the baseline visit and events present at Baseline that do not increase in severity during treatment will be considered as Baseline adverse events and will not be included in the presentation of TEAEs. If the date of a new AE does not allow for determination of whether the AE is treatment emergent, it will be assumed to be a TEAE.

The number and percentage of subjects experiencing TEAEs will be presented for the Safety Population for each body system and preferred term by treatment, and for each severity and relationship to study medication. When an adverse event occurs more than once, the maximum severity grade and relationship will be counted. For severity, only "Mild" and "Moderate" will be included for all SOCs and PTs; "Severe", "Life-Threatening", or "Fatal" will be included for SOCs and PTs only when such are recorded for severity. Similarly, only "Possibly Related" and "Not Related" will be included for all SOCs and PTs; "Definitely Related" and "Probably Related" will be included for SOCs and PTs when such are recorded for relationship.

Serious adverse events and discontinuations due to an adverse event will be provided in separate listings for the Safety Population. Each serious adverse event (SAE) will be listed for subjects in the Safety Population.

